6.2 Run-in Period

6.2.1 Visit 2 (Week -4)

During this visit the following procedures and assessments will be performed:

- Discuss and check compliance to standard of care specifics as per ADA 2017 guidelines, self-management of diabetes and life-style modifications with the subject
- Record concomitant medications since previous visit
- Record vital signs (sitting after 5 minutes rest; pulse, blood pressure, temperature and respiratory rate)
- Record AEs, SAEs, local and systemic allergic reactions and hypoglycemic events since the previous visit
- Collect blood sample for fasting plasma glucose
- Dispense subject diary to the subject and provide information regarding the completion requirements and necessary glucose measurements provided.
- Review current dosing of Lantus and Humalog and if necessary provide new dosing instructions and document the new dose and reason for change
- Dispense study medication and provide dose and titration instructions
- Dispense ancillary supplies

6.2.2 Visit 3 (Week -3), Visit 5 (Week -1)

These visits can be performed as telephone contacts if preferred by site and subject. If the visit is performed as a telephone contact, a time and date must be agreed in advance by both parties and the subject must have the completed subject diary available for discussion of the entries during the call.

During this visit the following procedures and assessments will be performed:

- Discuss and check compliance to standard of care specifics as per ADA 2017 guidelines, self-management of diabetes and life-style modifications with the subject
- Record concomitant medications since previous visit
- Record AEs, SAEs, local and systemic allergic reactions and hypoglycemic events since the previous visit
- Record device safety information
- Review the results of 8-point SMBG measurements, performed on 3 days during the week
- Review current dosing of Lantus and Humalog and if necessary provide new dosing instructions and document the new dose and reason for change

6.2.3 Visit 4 (Week -2)

During this visit the following procedures and assessments will be performed:

- Discuss and check compliance to standard of care specifics as per ADA 2017 guidelines, self-management of diabetes and life-style modifications with the subject
- Record concomitant medications since previous visit
- Record vital signs (sitting after 5 minutes rest; pulse, blood pressure, temperature and respiratory rate)
- Record AEs, SAEs, local and systemic allergic reactions and hypoglycemic events since the previous visit
- Record device safety information
- Collect blood sample for fasting plasma glucose
- Review the results of 8-point SMBG measurements, performed on 3 days during the week
- Review current dosing of Lantus and Humalog and if necessary provide new dosing instructions and document the new dose and reason for change
- Perform drug accountability and check for treatment compliance
- Review subject diary and provide information regarding the completion requirements and necessary glucose measurements provided.

6.3 Treatment phase

6.3.1 Visit 6 (Week 0)

After completion of the run-in phase without any major violation of the selection criteria the subjects will enter the randomized study treatment phase. During this visit the following procedures and assessments will be performed:

- Check selection criteria suitability
- Discuss and check compliance to standard of care specifics as per ADA 2017 guidelines, self-management of diabetes and life-style modifications with the subject
- Record body weight and calculate BMI
- Record concomitant medications since previous visit
- Record vital signs (sitting after 5 minutes rest; pulse, blood pressure, temperature and respiratory rate)
- Perform and document physical examination
- Perform 12-lead ECG (supine, after 5 minutes rest) and document results
- Record AEs, SAEs, local and systemic allergic reactions and hypoglycemic events since the previous visit
- Record device safety information
- Collect blood and urine samples for the following laboratory assessments:
 - Serum and urine pregnancy test for women of childbearing potential (only a negative urine test result is needed for dispensing drug)
 - Fasting plasma glucose
 - HbA1c
 - Hematology
 - Blood chemistry
 - Urine analysis
 - Fasting lipid profile
 - Immunogenicity analysis (collect blood sample prior to study drug administration)
 - PK analysis (collect blood sample prior to study drug administration)

- Review the results of 8-point SMBG measurements, performed on 3 days during the week
- Review current dosing of Lantus and Humalog and if necessary provide new dosing instructions and document the new dose and reason for change
- Dispense study medication MYL-1501D (product from Process VI or Process V), and Humalog
- Perform drug accountability and check for treatment compliance
- Review subject diary and provide information regarding the completion requirements and necessary glucose measurements provided.
- Perform randomization and document result

6.3.2 Visit 7 (Week 1), Visit 9 (Week 4), Visit 11 (Week 9)

These visits can be performed as telephone contacts if preferred by site and subject. If the visit is performed as a telephone contact, a time and date must be agreed in advance by both parties and the subject must have the completed subject diary available for discussion of the entries during the call.

During this visit the following procedures and assessments will be performed:

- Discuss and check compliance to standard of care specifics as per ADA 2017 guidelines, self-management of diabetes and life-style modifications with the subject
- Record concomitant medications since previous visit
- Record AEs, SAEs, local and systemic allergic reactions and hypoglycemic events since the previous visit
- Record device safety information
- Review current dosing of MYL-1501D (product from Process VI or Process V) and Humalog and if necessary provide new dosing instructions and document the new dose and reason for change

6.3.3 Visit 8 (Week 2), Visit 10 (Week 6)

During this visit the following procedures and assessments will be performed:

- Discuss and check compliance to standard of care specifics as per ADA 2017 guidelines, self-management of diabetes and life-style modifications with the subject
- Record concomitant medications since previous visit
- Record vital signs (sitting after 5 minutes rest; pulse, blood pressure, temperature and respiratory rate)
- Record AEs, SAEs, local and systemic allergic reactions and hypoglycemic events since the previous visit
- Record device safety information
- Collect blood and urine samples for the following laboratory assessments:
 - Urine pregnancy test for women of childbearing potential (only a negative urine test result is needed for dispensing drug)
 - Fasting plasma glucose
 - Immunogenicity analysis (collect blood sample prior to study drug administration as outlined in [Table 1](#))
 - PK analysis (collect blood sample prior to study drug administration as outlined in [Table 1](#))

- Review the results of 8-point SMBG measurements, performed on 3 days during the week, only for visit 10.
- Review current dosing of MYL-1501D (product from Process VI or Process V) and Humalog and if necessary provide new dosing instructions and document the new dose and reason for change
- Perform drug accountability and check for treatment compliance
- Review subject diary and provide information regarding the completion requirements and necessary glucose measurements provided.
- Only applicable to Visit 10, Dispense study medication MYL-1501D (product from Process VI or Process V) and Humalog

6.3.4 Visit 12 (Week 12)

During this visit the following procedures and assessments will be performed:

- Discuss and check compliance to standard of care specifics as per ADA 2017 guidelines, self-management of diabetes and life-style modifications with the subject
- Record concomitant medications since previous visit
- Record vital signs (sitting after 5 minutes rest; pulse, blood pressure, temperature and respiratory rate)
- Record AEs, SAEs, local and systemic allergic reactions and hypoglycemic events since the previous visit
- Record device safety information
- Collect blood and urine samples for the following laboratory assessments:
 - Urine pregnancy test for women of childbearing potential (only a negative urine test result is needed for dispensing drug)
 - Fasting plasma glucose
 - HbA1c
 - Fasting lipid profile
 - Immunogenicity analysis (collect blood sample prior to study drug administration as outlined in [Table 1](#))
 - PK analysis (collect blood sample prior to study drug administration as outlined in [Table 1](#))
- Review the results of 8-point SMBG measurements, performed on 3 days during the week
- Review current dosing of MYL-1501D (product from Process VI or Process V) and Humalog and if necessary provide new dosing instructions and document the new dose and reason for change
- Dispense study medication MYL-1501D (product from Process VI or Process V) and Humalog
- Perform drug accountability and check for treatment compliance
- Review subject diary and provide information regarding the completion requirements and necessary glucose measurements provided

6.3.5 Visit 13 (Week 15)

During this visit the following procedures and assessments will be performed:

- Discuss and check compliance to standard of care specifics as per ADA 2017 guidelines, self-management of diabetes and life-style modifications with the subject
- Record concomitant medications since previous visit
- Record AEs, SAEs, local and systemic allergic reactions and hypoglycemic events since the previous visit
- Record device safety information
- Collect blood and urine samples for the following laboratory assessments:
 - Serum and urine pregnancy test for women of childbearing potential (only a negative urine test result is needed for dispensing drug)
- Review current dosing of MYL-1501D (product from Process VI or Process V) and Humalog and if necessary provide new dosing instructions and document the new dose and reason for change
- Perform drug accountability and check for treatment compliance

6.3.6 Visit 14/ End of Treatment (Week 18)

During this visit the following procedures and assessments will be performed:

- Discuss and check compliance to standard of care specifics as per ADA 2017 guidelines, self-management of diabetes and life-style modifications with the subject
- Record body weight and calculate BMI
- Record concomitant medications since previous visit
- Record vital signs (sitting after 5 minutes rest; pulse, blood pressure, temperature and respiratory rate)
- Perform 12-lead ECG (supine, after 5 minutes rest) and document results
- Record AEs, SAEs, local and systemic allergic reactions and hypoglycemic events since the previous visit
- Record device safety information
- Collect blood and urine samples for the following laboratory assessments:
 - Urine pregnancy test for women of childbearing potential (only a negative urine test result is needed for dispensing drug)
 - Fasting plasma glucose
 - HbA1c
 - Hematology
 - Blood chemistry
 - Urine analysis
 - Fasting lipid profile
 - Immunogenicity analysis (collect blood sample prior to study drug administration as outlined in [Table 1](#))
 - PK analysis (collect blood sample prior to study drug administration as outlined in [Table 1](#))
- Review the results of 8-point SMBG measurements, performed on 3 days during the week
- Review current dosing of MYL-1501D (product from Process VI or Process V) and Humalog and if necessary provide new dosing instructions and document the new dose and reason for change
- Perform drug accountability and check for treatment compliance
- Review subject diary and provide information regarding the completion requirements and necessary glucose measurements provided

6.3.7 Early study drug Termination (ET) visit

Subjects may request termination of study drug or withdrawal from the study at any time, or be required to withdraw or terminate study drug by the investigator or sponsor for reasons as per Section 4.3.4. If study drug is terminated or the subject withdraws or is withdrawn, the reason for termination/withdrawal should be established and recorded. If a subject does not return for a scheduled visit, every effort should be made to contact the subject. In any circumstance, every effort should be made to document the outcome of subject contact attempt, if possible. The investigator will contact Mylan or designee, if subject fails to complete the study or violates the protocol.

If the subject withdraws from the study and also withdraws consent for disclosure of future information, no further evaluations should be performed and no additional data should be collected. The sponsor may retain and continue to use any data collected before such withdrawal of consent.

Unless consent is withdrawn, subjects who prematurely terminate study drug will be asked to return to the clinic to conduct the ET visit as soon as possible after their last dose of study drug, and in case consent subject will be asked to conduct all the remaining visits according to study schedule table until the end of the study.

At the ET visit the End of Treatment visit (Week 18/Visit 14), procedures should be completed.

The site should explain the importance of data collection and make every effort to consent the subject to continue follow up per the SCHEDULE OF ACTIVITIES until Week 20 visit.

6.4 Visit 15 Follow up (Week 20) (telephone call)

- Record AEs, SAEs, local and systemic allergic reactions and severe hypoglycemic which are classified as SAE.
- Record concomitant medications since previous visit

6.5 Treatment Procedures

Every effort should be made to ensure that the protocol required tests and procedures are completed as described. However, it is anticipated that from time to time there may be circumstances, outside of the control of the investigator that may make it unfeasible to perform the test. In these cases, the investigator or designated representative will take all steps necessary to ensure the safety and well-being of the subject. When a protocol required test cannot be performed the investigator or designated representative will document the reason for this and any corrective and preventive actions which he/she has taken to ensure that normal processes are adhered to as soon as possible. The Mylan study team will be informed of these incidents in a timely fashion.

Activities specific to this protocol are expanded upon further below.

6.5.1 Blood Volume

Total blood sampling volume for an individual subject is approximately 235 mL.

Table 3: Blood Volume

Sample Type	Sample Volume (mL)	Number of Sampling Times		Total Volume (mL)
		Screening	Study Period	
Safety Labs	30	1	3	120
PK ¹	4		5	20
Anti-drug antibody (ADA) ²	10	1	5	60
Supplemental Immunogenicity ³	10 (baseline), 5 (V1, V8, V10, V12, V14)	1	5	35
TOTAL				235

¹ Blood samples (1 x 4 mL) will be drawn into K₂EDTA plasma tubes.

² Blood samples (2 x 5 mL) will be drawn into serum separator tubes (SST).

³ Blood samples (1 x 5 mL; 2 x 5 mL at baseline) will be drawn into serum separator tubes (SST).

6.5.2 Safety Testing Assessments

Safety will be assessed through physical examinations, monitoring of vital signs, 12-lead electrocardiograms, laboratory analyses, and adverse event monitoring.

6.5.2.1 Adverse Event Assessment

If a subject reports any symptoms after the signing of the informed consent form, they will be evaluated by medical staff and necessary measurements will be performed. The Principal Investigator or Medical Sub-Investigator will be notified before dosing to determine the course of action.

Clinically relevant findings from screening procedures, e.g., laboratory tests or physical examinations will be recorded as medical history. Clinically significant changes from the screening procedures results will be recorded as adverse events.

Subjects will be routinely queried with regard to the presence or absence of adverse events using open ended questions. The clinic will provide documentation of any adverse events in the subject's CRF. The adverse event source documentation will minimally include the following information: date and time of assessment, the outcome of the response, and identification of the clinic staff member collecting the information.

6.5.2.2 Hypoglycemia

Incidence of hypoglycemic episodes will also be summarized by category (Severe Hypoglycemia, Documented Symptomatic Hypoglycemia, Asymptomatic Hypoglycemia, Probable Symptomatic Hypoglycemia, Relative Hypoglycemia and Nocturnal Hypoglycemia). In addition, nocturnal hypoglycemia rate and incidence will be analyzed in a same way as overall hypoglycemic episodes.

Hypoglycemia is a state produced by a lower than normal level of glucose in the blood. This may develop, if for example:

- The subject misses or delays meals or there is a change in diet
- The subject takes a higher dose of study drug than prescribed
- The subject consumes alcohol
- The subject does more intense or longer physical exercise or work than normal,

- The subject is recovering from an injury, operation, fever or other illness, or from other forms of stress

6.5.2.2.1 Classification

A. Severe Hypoglycemia

An event is considered as severe hypoglycemia if it requires the assistance of another person to actively administer carbohydrate, glucagon, or other resuscitative actions which results in neurological recovery, regardless of the availability of a blood glucose measurement. These episodes may be associated with sufficient neuroglycopenia to induce seizure or coma. Plasma glucose measurements may not be available during such an event, but neurological recovery attributable to the restoration of normal plasma glucose is considered sufficient evidence that the event was induced by a low plasma glucose concentration.

B. Documented Symptomatic Hypoglycemia

An event during which typical symptoms of hypoglycemia are accompanied by a measured plasma glucose concentration ≤ 70 mg/dL (3.9 mmol/L).

C. Asymptomatic Hypoglycemia

An event not accompanied by typical symptoms of hypoglycemia but with a measured plasma glucose concentration ≤ 70 mg/dL (3.9 mmol/L).

D. Probable Symptomatic Hypoglycemia.

Characteristic symptoms of hypoglycemia with no blood glucose level measurement that resolved with food intake, subcutaneous glucagon, or intravenous glucose.

E. Relative Hypoglycemia.

An event during which the subject reports any of the typical symptoms of hypoglycemia, and interprets the symptoms as indicative of hypoglycemia, but with a measured plasma glucose concentration > 70 mg/dL (3.9 mmol/L).

F. Nocturnal Hypoglycemia.

Nocturnal hypoglycemia will include hypoglycemia that occurs from the time the subject goes to bed at night till the time he or she wakes up. This may include any of the above 5 types of hypoglycemia.

Note: A diagnosis of severe hypoglycemia as per above classification will always be considered as serious adverse event. Other hypoglycemic episodes which fulfils ICH criteria for seriousness (life-threatening, hospitalization etc.) or represent important medical events based on investigator's judgment should also be reported to sponsor within 24 hours.

6.5.2.2.2 Identification of Hypoglycemia

Symptoms of hypoglycemia include but are not limited to the following: palpitations, sweating, hunger, nervousness and shakiness, perspiration, dizziness or light-headedness,

sleepiness, confusion, difficulty speaking, feeling anxious or weak. Neuroglycopenic manifestations may include seizure, coma, and even death.

Subject will be instructed to be alert for signs and symptoms of hypoglycemia; and if possible to take glucose meter readings at the time of the episode and to record the details of the episode with any remedial action taken and the blood glucose level (if it was checked) in their diary.

Investigators will instruct the subjects on self-management of hypoglycemic episodes. Investigators will also instruct subjects on remedial actions to be taken during the episodes of severe hypoglycemia. Subject will be encouraged to call the study site if they experience hypoglycemia.

6.5.2.2.3 Management of Hypoglycemia

The following steps are recommended for managing hypoglycemic episodes:

1. The subject should begin with 15 to 20 grams carbohydrate (e.g., 3-4 teaspoons of table sugar dissolved in water, 1 tablespoon of honey, $\frac{3}{4}$ cup of juice or regular soft drink, 3-4 glucose tablets).
2. Subsequently, if the glucose level is ≤ 50 mg/dL, then the subject will be asked to consume 20 to 30 grams carbohydrate (e.g., 4-6 teaspoons of table sugar dissolved in water, 2 tablespoons of honey, $\frac{3}{4}$ cup of juice or regular soft drink, 4-5 glucose tablets).
3. Subject will be asked to recheck blood glucose after 15 minutes and to repeat hypoglycemia treatment if the blood glucose does not return to normal after 15 minutes. If the next meal is more than 1 hour away, subjects should follow with additional carbohydrate or a snack.
4. If hypoglycemia persists after the second treatment, subject or companion should be instructed to contact the investigator.

It is recommended that the subjects always carry some sugar lumps, sweets, biscuits, or sugary fruit juice.

For an event of severe hypoglycemia, the subject can be treated with glucagon (0.5 to 1 mg) given intramuscularly or subcutaneously by a person who has received appropriate training, or glucose given intravenously by a medical professional. Intravenous glucose can also be given if the subject does not respond to glucagon within 10 to 15 minutes. Upon regaining consciousness administration of oral carbohydrate is recommended in order to prevent a relapse.

Full hypoglycemic episode documentation includes time of occurrence, duration, time of recovery, remedial measures undertaken, recording the symptoms and plasma glucose / SMBG levels at the beginning and end of the episode with time and date, and classification in to the different subtypes (Refer to [Section 6.5.2.2.1](#)).

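### The step 2 hypoglycemia instruction keeps the same 3/4 cup of juice or soft drink that step 1 gives for a smaller dose, so the drink may fall up to 5 g short of the 20 g minimum

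*Protocol*

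**What the plan says.** Section 6.5.2.2.3 (Management of Hypoglycemia) of Protocol Version 2.0 recommends four steps.

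- **Step 1:** "The subject should begin with 15 to 20 grams carbohydrate". The household examples are 3-4 teaspoons of sugar in water, then "1 tablespoon of honey, $\frac{3}{4}$ cup of juice or regular soft drink, 3-4 glucose tablets".
- **Step 2:** if glucose is at or below 50 mg/dL, "then the subject will be asked to consume 20 to 30 grams carbohydrate". The examples are 4-6 teaspoons of sugar in water, then "2 tablespoons of honey, $\frac{3}{4}$ cup of juice or regular soft drink, 4-5 glucose tablets".
- **Step 3:** "Subject will be asked to recheck blood glucose after 15 minutes and to repeat hypoglycemia treatment" if glucose has not returned to normal.
- **Step 4:** "If hypoglycemia persists after the second treatment, subject or companion should be instructed to contact the investigator".

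The section also says: "It is recommended that the subjects always carry some sugar lumps, sweets, biscuits, or sugary fruit juice". Section 6.5.2.2.2 adds: "Investigators will instruct the subjects on self-management of hypoglycemic episodes".

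Version 1.0 of the protocol lists the same drink volume in both steps. Neither the protocol nor the SAP gives a carbohydrate content for the drink or a different volume.

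**The concern.** The household examples turn a gram target into something a subject can measure at home, so each should deliver the target it illustrates. Step 2 raises the target, and three of its four examples rise with it. The drink stays at 3/4 cup. One volume cannot illustrate both 15-20 g and 20-30 g unless it holds exactly 20 g, and even then it reaches only the bottom of the step 2 range.

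What is at stake is patient safety. Step 2 covers the lower glucose values in people with type 1 diabetes, and section 6.5.2.2.2 lists confusion among the symptoms and seizure and coma among the neuroglycopenic manifestations. Juice is a foreseeable choice, because it is one of four kinds of item that subjects are advised to carry. The documents do not say how often it is used.

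**Working it through.** **Inputs**, all from steps 1 and 2 of section 6.5.2.2.3:

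| | Step 1 | Step 2 | Change (low end, high end) |
|---|---|---|---|
| Target | 15-20 g | 20-30 g | +33%, +50% |
| Sugar | 3-4 teaspoons | 4-6 teaspoons | +33%, +50% |
| Honey | 1 tablespoon | 2 tablespoons | +100% |
| Tablets | 3-4 | 4-5 | +33%, +25% |
| Drink | 3/4 cup | 3/4 cup | 0% |

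**Assumption.** Each step 1 example supplies step 1's range. For the drink, 3/4 cup then holds c grams, with c between 15 and 20. No outside nutrition figure is used.

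**Does step 1's equivalence reproduce step 2's target?**

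- Sugar: 15/3 = 20/4 = 5 g per teaspoon, so 4-6 teaspoons give 4 × 5 = 20 g to 6 × 5 = 30 g. This reproduces 20-30 g exactly.
- Tablets: 15/3 = 20/4 = 5 g each, so 4-5 tablets give 20-25 g, inside the range.
- Honey: 15-20 g per tablespoon, so 2 tablespoons give 30-40 g, at or above the top of the range.
- Drink: unchanged at 15-20 g, at or below the bottom of the range.

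**Shortfall of the drink against the 20 g minimum**, 20 − c:

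- c = 15: 20 − 15 = 5 g, and 5/20 = 25%
- c = 17.5: 20 − 17.5 = 2.5 g, and 2.5/20 = 12.5%
- c = 20: no shortfall

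Against the 30 g upper end, the drink is 30 − 20 = 10 g to 30 − 15 = 15 g below.

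**Volume that would meet step 2.** The cups needed for 20 g are 0.75 × 20/c:

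- c = 15: 1.0 cup
- c = 17.5: 0.857 cup
- c = 20: 0.75 cup

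One cup supplies c/0.75:

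- c = 15: 20.0 g
- c = 17.5: 23.3 g
- c = 20: 26.7 g

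All three values lie within 20-30 g.

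**The case against.** Five points can be made for leaving the text alone.

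1. **The ranges meet at 20 g.** If 3/4 cup holds about 20 g, both steps are right as written, and the documents do not say otherwise. This stands, and it is why the finding is a possible shortfall of 0 to 5 g and not a proven one.
2. **These are rough examples, and honey misses too.** On the same logic, 2 tablespoons of honey give 30-40 g, which meets the 30 g maximum at one value only and otherwise exceeds it by up to 10 g. That is a fair test of the method. But any honey error is towards more carbohydrate, the less worrying direction in hypoglycemia, and it does not make the drink example right.
3. **The gram target governs.** Step 2 states 20-30 g explicitly. This limits the harm, but a subject following the household measure would still take the listed volume.
4. **Step 2 may be taken on top of step 1.** The wording supports that reading, and a juice user would then have had 30-40 g in all. This reduces the practical consequence. It does not change the comparison of the step 2 drink with step 2's own target.
5. **There are safeguards.** The steps are recommendations. Glucose is rechecked after 15 minutes, persistent hypoglycemia prompts contact with the investigator, and severe events have separate glucagon and intravenous glucose instructions. Subjects are trained in self-management (Table 1, footnote 2) and have had at least a year of basal-bolus therapy (section 4.2.1, criterion 3b). All of this stands and keeps the matter minor.

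**Conclusion.** The concern holds as a minor patient-safety correction that should be made. The same volume appears under two targets that share only one value, and the drink is the only example that does not increase. Taking 3/4 cup as 15-20 g, the step 2 drink is 0 to 5 g (0 to 25%) below the stated minimum. The inconsistency in the text is certain. The size of any actual shortfall depends on that assumption, because the protocol states no gram content. A text-extraction error is unlikely, since both protocol versions carry the same volume. Endpoints, sample size and analysis are not affected.

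**What to change.** In step 2 of section 6.5.2.2.3, change the juice or soft drink example from 3/4 cup to about 1 cup, and have the sponsor's medical team confirm the volume, because the 1 cup figure rests on the same 15-20 g assumption. The rest of step 2 can stay as it is, although the medical team could look at the honey example at the same time. Carry the corrected volume into any subject instructions that repeat it.

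The cost is one figure in one step, plus any matching subject instruction. No data collection or analysis changes.
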